7.9.7.2 Secondary Efficacy Analyses

The percent change from Baseline to Week 12 in inflammatory and non-inflammatory lesion counts will be analyzed using the same ANCOVA method described for the primary endpoint.

The proportion of subjects who are dichotomized to success (minimum 2-grade improvement from Baseline) at Week 12 will be analyzed using the same logistic analysis method described for the primary endpoint. A stepwise process will be conducted for testing the secondary efficacy endpoints in order to control for multiplicity, refer to Section 7.6 for details.

7.9.7.3 Other Supportive Efficacy Analyses

The percent change and absolute change from Baseline to Weeks 4 and 8 inflammatory and non-inflammatory lesion counts will be analyzed using the same ANCOVA method described for the primary endpoint of absolute change in lesion counts from Baseline to Week 12. The inclusion of p-values in these efficacy analyses is to assist in characterizing the therapeutic efficacy of the active formulation and dosage regimen. No adjustments will be made for multiple comparisons for the supportive efficacy analyses.

Descriptive statistics will be presented for the following parameters by treatment group for both the ITT and PP populations:

- Frequency and percent distributions of the IGA Score at Baseline and Weeks 4, 8 and 12;
- Frequency and percent distributions of the dichotomized IGA Score at Baseline and Weeks 4, 8 and 12;
- Descriptive statistics will be used to summarize inflammatory and non-inflammatory lesion counts at Baseline and Weeks 4, 8 and 12;
- Descriptive statistics will be used to summarize the absolute and percent change in inflammatory and non-inflammatory lesion counts at Weeks 4, 8 and 12;
- Descriptive statistics will be used to summarize the Acne Patient Self-Questionnaire assessments at Weeks 4, 8 and 12. Satisfaction questions answered at Week 12 will be summarized with frequency and percent distributions.

7.9.8 Safety Analyses

7.9.8.1 Extent of Exposure

The extent of exposure to study drug in each treatment group will be summarized by amount of study drug used (computed from study drug tube weights) and anatomical areas treated. Facial exposure will be summarized by total number of days of exposure, total number of applications, number of missed applications and number and percentage of subjects who are compliant. A subject will be considered compliant with the dosing regimen if the subject applied 80% to 120% of the expected number of applications while enrolled in the study. Total number of days of exposure will be computed as follows:

$$\text{Total Exposure} = \text{Date of Last Application} - \text{Date of First Application} + 1.$$

Dosing deviations reported for areas other than the face will not be considered in compliance calculations. On the date of first application and the date of last application, some subjects were to apply one dose and others were to apply two doses, depending on the time of the study visit. After the date of first application and before the date of last application subjects were expected to

apply two doses. Missed applications will be calculated from dosing deviations which report zero or one application on a given date. Extra doses will be calculated from dosing deviations which report more than the expected number of applications on a given date. The total number of applications will be calculated as follows:

If the Date of First Application is not equal to Date of Last Application, then

$$\begin{aligned} \text{Total Applications} &= 2 * (\text{Date of Last Application} - \text{Date of First Application} - 1) \\ &+ \text{Expected Applications on Date of First Application} \\ &+ \text{Expected Applications on Date of Last Application} \\ &- \text{Missed Applications} + \text{Extra Applications.} \end{aligned}$$

If the Date of First Application = Date of Last Application, then

$$\begin{aligned} \text{Total Applications} &= \text{Expected Applications on Date of First Application} \\ &- \text{Missed Applications} + \text{Extra Applications.} \end{aligned}$$

Treatment compliance will be based on the expected number of doses given the treatment period duration. Treatment period duration will be computed from the Baseline/Day 1 visit date and the Week 12/Early Termination (ET) visit date. If a subject does not have a Week 12/ET visit, treatment period duration will be calculated based on the date of last dose or last completed visit date, whichever is later. That is, treatment period duration will be computed from the Baseline/Day 1 date and the end of treatment period date, where the end of treatment period date is given by

- If the subject completed the Week 12/ET visit, the end of treatment period date will be:
 - The date of the Week 12/ET visit if the expected number of applications on the date of last application is one;
 - The day prior to the Week 12/ET visit if the expected number of applications on the date of last application is two;
- If the subject did not complete the Week 12/ET visit, the end of treatment period date will be the date of last dose or last completed visit, whichever is later.

Then treatment period duration may be calculated as:

$$\text{Treatment Period Duration} = \text{End of Treatment Period Date} - \text{Day 1 Date} + 1.$$

If the treatment period duration exceeds 88 days, treatment period duration will be considered 88 days. In addition to treatment period duration, missed applications due to treatment-related AEs will be considered when determining the expected number of doses for each subject. If a treatment-related AE (regardless of location) requires interruption of study drug during the

treatment period, missed applications during the AE (onset date to resolution date) will be deducted from the expected number of doses. Therefore, the expected number of applications will be calculated as:

$$\begin{aligned} \text{Expected Applications} &= 2 * (\text{Treatment Period Duration} - 2) \\ &+ \text{Expected Applications on Date of First Application} \\ &+ \text{Expected Applications on Date of Last Application} \\ &- \text{Applications Missed Due to a Treatment-Related AE.} \end{aligned}$$

If Treatment Period Duration = 1, then

$$\begin{aligned} \text{Expected Applications} &= \text{Expected Applications on Date of First Application} \\ &- \text{Applications Missed Due to a Treatment-Related AE.} \end{aligned}$$

Percent compliance will be calculated from total number of applications and total number of expected applications as follows:

$$\text{Percent Compliance} = 100 * (\text{Total Applications} / \text{Expected Applications}).$$

Percent compliance will not be calculated for subjects who are lost to follow-up.

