9.4.8 Dosing Changes due to AEs

Dose interruptions are allowed should a subject experience intolerable treatment-related adverse events (e.g., pruritis) on study. In cases where the Investigator feels a dose interruption is warranted, the subject should be instructed to interrupt study drug application to allow symptoms to resolve. Subjects should be instructed to return to the twice daily application regimen within 2 days of dose interruption.

Dosing interruptions are to be recorded in the subject diary as a missed dose.

Study drug must be discontinued if an adverse event is deemed persistent and if continuation of study drug would not be in the best interest of the subject.

Refer to Section 10.3 for further information regarding discontinuation of study drug or early withdrawal.

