11.10 Exposure and Compliance

The extent of exposure to study drug in each treatment group will be summarized by total number of days of exposure, total number of applications, number of missed applications and number and percentage of subjects who are compliant. A subject will be considered compliant

with the dosing regimen if the subject applied 80% to 120% of the expected number of applications while enrolled in the study.

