7.8.4 Per-Protocol (PP) Population

All subjects in the safety population who complete the Week 12 evaluation without any significant protocol violations will be included in the PP population and analyzed according to the treatment group they received. The PP population will include subjects in the safety population who do not meet any of the following criteria:

- Violated the inclusion/exclusion criteria;
- Have taken any interfering concomitant medication;
- Did not attend the Week 12 visit;
- Have missed both the Week 4 and Week 8 study visits;
- Have not been compliant with the dosing regimen (i.e. subjects must apply 80-120% of the expected applications of study medication during participation in the study);
- Out of visit window at the Week 12 visit by ± 5 days.

Subjects that discontinue treatment or from the study due to an AE related to study treatment or documented lack of treatment effect will be included in the PP population. Prior to breaking the blind, other additional criteria may be added to the list to accommodate for unforeseen events that occurred during the conduct of the trial that result in noteworthy study protocol violations.

All efficacy analyses will be performed on the PP population.

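### Percent compliance sets applications counted to the actual last dose against expected applications capped at 88 days, and drops related-AE misses from both parts; the per-protocol effect is small for the cap and unknown for the AE rule

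*SAP*

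**What the plan says.** SAP 7.9.8.1 builds percent compliance from two counts.

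- **Total applications.** These run from the date of first application to the date of last application, less missed and plus extra applications. No upper date is set. "Missed applications will be calculated from dosing deviations which report zero or one application on a given date".
- **Expected applications.** These come from the treatment period duration. The period ends on the Week 12/ET visit date if one application is expected on the last application date, and on the day before the visit if two are expected. Then: "If the treatment period duration exceeds 88 days, treatment period duration will be considered 88 days". Where a treatment-related AE requires interruption of study drug, "missed applications during the AE (onset date to resolution date) will be deducted from the expected number of doses". No limit on that deduction is given.

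The result feeds the compliance summary and the PP set. Protocol 11.10 calls a subject compliant who "applied 80% to 120% of the expected number of applications while enrolled in the study", and SAP 7.8.4 repeats the band as a PP criterion: "subjects must apply 80-120% of the expected applications of study medication during participation in the study". The same PP list also excludes subjects "Out of visit window at the Week 12 visit by ± 5 days", and it keeps subjects who stop because of a related AE or documented lack of effect.

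Protocol 11.2 and 11.10 give the 80–120% rule but do not say how the expected number is derived. SAP Section 5, which lists changes from the protocol, mentions neither the cap nor the AE deduction.

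**The concern.** A ratio of applications taken to applications expected should count both over the same days. Here only the denominator stops at 88 days, so anyone who keeps applying beyond that gains credit with nothing set against it. The cap can bind inside the protocol's own visit window, and Protocol Section 8 does not treat out-of-window visits as deviations, so longer periods are foreseeable.

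The AE deduction is a separate matter. Missed applications have already been subtracted from the total. Those that fall in a qualifying AE are then subtracted from the expected count as well, so they have no effect on the score of a subject with no other misses.

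At stake are the compliance table and membership of the PP set, on which all efficacy analyses are repeated (SAP 7.8.4 and 7.9.7). Because the deduction depends on related AEs, it could act differently in the two arms.

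**Working it through.** **Inputs.** Cap of 88 days, the two formulas and the end-of-period rule: SAP 7.9.8.1. Week 12 target day 85: SAP 7.9.2. Window ±4 days: Protocol 8.7. Band 80–120% and the ±5-day criterion: SAP 7.8.4. Planned regimen, twice daily for 12 weeks: 2 × 84 = 168 applications.

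**Origin of the cap.** 12 × 7 + 4 = 88; equally, 85 + 4 = day 89, and the day before that visit is day 88. The SAP does not explain the figure, so this is an inference.

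**Formulas.** With F and L the applications expected on the first and last dates:

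- Total = 2 × (last day − 2) + F + L − missed + extra
- Expected = 2 × (min(duration, 88) − 2) + F + L − AE-related misses

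**Step 1: full use, no AE.** With F = L = 1, the last application falls on the visit day, and Expected = 2 × 86 + 2 = 174 once the cap binds.

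| Week 12 visit | Total | Expected | Score |
|---|---|---|---|
| Day 89 | 2 × 87 + 2 = 176 | 174 | 101.1% |
| Day 90 | 2 × 88 + 2 = 178 | 174 | 102.3% |
| Day 94 | 2 × 92 + 2 = 186 | 174 | 106.9% |
| Day 106 | 2 × 104 + 2 = 210 | 174 | 120.7% |

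These are upper values. With F = L = 2 the period ends the day before the visit: day 89 gives 176/176 = 100.0%, day 94 gives 186/176 = 105.7%, and day 106 gives 210/176 = 119.3%, still inside the band. Full use then passes 120% at day 107 (212/176 = 120.5%).

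**Step 2: what this does to the 80% floor.** Once the cap binds, Expected is 174 to 176. The lowest whole count that passes is 140 (0.80 × 174 = 139.2; 0.80 × 175 = 140) or 141 (0.80 × 176 = 140.8). Against the applications due over the actual period:

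- Day 90, the latest day if ±5 is taken around day 85: 140/179 = 78.2% (F = 2, L = 1) to 141/178 = 79.2% (F = L = 2).
- Day 94, the latest day if 5 days are added to the ±4 window: 140/187 = 74.9% to 141/186 = 75.8%.

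So the floor drops by about 2 or 5 points at most. Against the planned course, 140/168 = 83.3% and 141/168 = 83.9%.

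**Step 3: AE deduction.** Visit on day 85, F = L = 2, 84 days, 168 expected before any deduction.

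| AE misses | Other misses | Score under SAP | Score without deduction |
|---|---|---|---|
| 4 | 0 | 164/164 = 100% | 164/168 = 97.6% |
| 34 | 0 | 134/134 = 100% | 134/168 = 79.8% |
| 84 | 0 | 84/84 = 100% | 84/168 = 50.0% |
| 28 | 28 | 112/140 = 80.0% | 112/168 = 66.7% |

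With AE misses only, 34 is the first count at which the classification changes, since 0.80 × 168 = 134.4.

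**The case against.** **The cap.** A reader might infer that the cap brings under-dosed subjects into the PP set. The documents do not support that. A visit on day 98 or day 106 is 13 or 21 days past day 85, so the Week 12 timing criterion removes the subject whatever the score. Subjects who remain and pass because of the cap have taken at least 140 of the planned 168 applications. The cap also has a plausible purpose: each kit is packed for 12 weeks (Protocol 6.2), and without a cap a subject who finishes on time but attends late would be penalised. This part stands, and it argues for keeping the cap and aligning the numerator with it.

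**The AE rule.** A reader might also infer that the deduction contradicts the protocol. It does not clearly do so. The protocol never defines the expected number, so any score without the deduction is one possible reading and not the protocol's definition. The protocol's instruction, "Dosing interruptions are to be recorded in the subject diary as a missed dose", concerns diary recording, and the SAP follows it: those doses still count as missed and still reduce total applications. The deduction also fits the retention in PP of subjects who discontinue for a related AE. Removing it could exclude a subject who interrupts and completes while keeping one who stops for the same reaction. That stands, so which version should define PP is a judgement.

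**Length of interruptions.** Protocol 9.4.8 says subjects should be instructed to resume within 2 days, about 4 applications, which moves the score by only 2.4 points. That stands for typical cases. It is not a bound, because the deduction window is the AE's onset to resolution and the formula carries no limit.

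**Visibility.** Total and missed applications and tube-weight use are summarised by arm, as are AEs by relatedness and local skin reactions. Poor tolerability would therefore not be hidden, although the compliance percentage alone would not show it.

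**Conclusion.** The mismatch of periods is real and follows directly from the SAP formulas. Full use scores up to 101.1% at day 89, 106.9% at day 94 and 120.7% at day 106, where complete use is labelled non-compliant. Within PP the effect is limited to about 2 to 5 points of the 80% floor, depending on how the ±5-day criterion is read; later visits affect only the compliance table.

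The AE deduction is unlimited as written: a subject with only related-AE misses scores 100% even when 34 or more of 168 planned applications were missed. It is nevertheless an explicit, pre-specified rule.

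The documents give no rate or length of interruptions, so the number of subjects affected is unknown. An imbalance between arms is possible but not shown. The nearest figure, four treatment-related drug discontinuations in the 420-subject Phase 2 dose-ranging study (Protocol 1.2), counts discontinuations and not interruptions. Compliance does not define the ITT population, and the stepwise secondary tests use ITT only (SAP 7.6), so ITT results are unaffected. This is a minor point that is worth correcting because it is cheap. The figures assume one or two applications on the first and last dates, as shown.

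**What to change.** Before unblinding, revise SAP 7.9.8.1 as follows.

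1. Count applications in the compliance numerator only up to the capped end date used for the denominator, and deduct AE-related misses only within that period.
2. Where the cap binds, use the same last-day term in both parts. Otherwise a residue remains: with F = 1, full use through day 88 is 1 + 2 × 86 + 2 = 175 against 174 expected.
3. Keep uncapped totals in the exposure table.
4. Report compliance with and without the AE deduction, and state which version defines PP.
5. List both rules in SAP Section 5, since the protocol's 80–120% rule mentions neither.

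The ±5-day criterion should also be tied to a study day, because the two readings differ by 4 days.

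The cost is a small derivation change, one further compliance summary, and slightly different reported compliance for subjects with late visits.

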7.9.8.2 Adverse Events

All AEs that occur during the study will be recorded and classified on the basis of MedDRA terminology. Treatment-emergent AEs (TEAEs) are defined as AEs with an onset on or after the date of the first study drug application. AEs noted prior to the first study drug administration that worsen after Baseline will also be reported as AEs and included in the summaries.

All information pertaining to an AE noted during the study will be listed by subject, detailing verbatim term given by the investigator or designee, preferred term, system organ class, onset date, resolution date, severity, seriousness, action taken, outcome and drug relatedness. The event onset will also be shown relative (in number of days) to date of first application.

Treatment-emergent AEs will be summarized by treatment group, the number of subjects reporting a TEAE, system organ class, preferred term, severity, relationship to study drug (causality) and seriousness. When summarizing AEs by severity and relationship, each subject will be counted once within a system organ class or a preferred term by using the event with the highest severity and greatest relationship within each classification.

Serious AEs (SAEs) will be summarized by treatment group, severity and relationship to study drug, and individual SAEs will be listed by subject. In addition, a summary of AEs leading to discontinuation from the study due will be provided.

No statistical inference between treatment groups will be performed on AEs.

Listings will be presented for all AEs as well as for SAEs and AEs leading to discontinuation from the study.

7.9.8.3 Clinical Laboratory Evaluations

Laboratory test results will be summarized descriptively at Baseline and Week 12. Additionally, shifts from Baseline to Week 12 in laboratory test results based on normal ranges will be summarized with descriptive statistics. Individual laboratory test results will be presented in a by-subject listing.

7.9.8.4 Local Skin Reactions

LSRs include erythema, peeling, dryness, burning/stinging and pruritus. These will be scored as 0 (None), 1 (Mild), 2 (Moderate) or 3 (Severe). LSRs will be summarized by treatment group and visit using descriptive statistics. Each subject's worst post-baseline grade for each LSR will also be summarized. Additionally, the number of subjects who experience mild, moderate or severe LSRs post-baseline will be presented. By-subject listing of all LSRs, as well as subjects with any severe LSRs will be included.

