8.1 Screening (Day -35 to -1)

The screening evaluation period may take up to 35 days in order to provide adequate washout time for subjects taking certain medications. The purpose of the screening visit is to ensure that appropriate subjects are entered into the study and remain stable during the pre-treatment period. Questions on eligibility will be referred to the Sponsor or their designee. Screen failures may be re-screened one time and must be assigned a new screening number. Screen failure information will be recorded in the eCRF. Screening procedures, excluding lab evaluations, may be done any time during the screening period (prior to dosing on Day 1) and after the subject has given informed consent.

- Obtain written informed consent/assent. For subjects under legal adult age, both parents or legal representatives may be required to sign informed consent as applicable.
- Collect demographic information
- Complete medical history
- Query subject for concomitant medication use
- Perform a complete physical examination
- Record height and weight
- Measure vital signs
- Assess Inclusion/Exclusion criteria
- Collect a 12 lead ECG
- Draw blood samples for laboratory tests and urine for urinalysis. Include serum pregnancy test for women of childbearing potential
- Determine concomitant medication washout duration
- Schedule next visit

8.2 Baseline Visit/ Day 1

Evaluations are to be done prior to the first dose of study drug

- Collect concomitant medication information
- Conduct a symptom-directed physical exam update medical history if appropriate
- Measure vital signs
- Conduct urine pregnancy test for women of childbearing potential
- Conduct Investigator Global Assessment (IGA)
- Collect acne lesion counts
- Collect Acne Patient Self- Questionnaire
- Evaluate face for pre-treatment local skin reactions (LSRs)
- Collect photographs (selected sites)
- Confirm subject eligibility (Inclusion/Exclusion criteria) and randomization to treatment
- Instruct subject on study medication application and diary completion
- Weigh tubes and dispense study drug and diary. Observe subject administering first dose
- Schedule all subsequent visits

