9.4.5 Local Skin Reactions (LSRs)

All subjects will be assessed for LSRs, on the face, at each visit. LSRs include burning/stinging, pruritus, erythema, dryness and peeling. Each LSR will be scored as 0 (None), 1 (Mild), 2 (Moderate) or 3 (Severe). LSRs observed on a visit day will not be recorded as adverse events

unless scored as 3 (Severe). Local skin reactions experienced by the subject in between study visits are to be recorded as an AE.

Burning/stinging and pruritus will be assessed by the subject (Table 3) and erythema, dryness and peeling will be assessed by the Investigator/designee (Table 4). Subjects will be read the definition of each subject-assessed LSR and asked to select the appropriate definition. The corresponding score will be assigned by the site and entered in the eCRF.

Table 3: Subject Assessed Local Skin Reactions

Score	Grade	Burning/Stinging	Pruritus
0	None	No stinging/burning	No pruritus
1	Mild	Slightly warm, tingling sensation; not really bothersome	Occasional, slight itching/scratching
2	Moderate	Definite warm; tingling/stinging sensation that is somewhat bothersome	Intermittent itching/scratching which does not disturb sleep
3	Severe	Hot, tingling/stinging sensation that has caused definite discomfort	Bothersome itching/scratching which disturbs sleep

Table 4: Investigator Assessed Local Skin Reactions

Score	Grade	Erythema	Dryness	Peeling
0	None	None	None	None
1	Mild	Slight erythema: very light- pink	Perceptible dryness with no flakes or fissure formation	Mild diffuse peeling
2	Moderate	Dull red, clearly distinguishable	Easily noted dryness and flakes but no fissure formation	Moderate diffuse peeling
3	Severe	Deep/dark red	Easily noted dryness with flakes and fissure formation	Moderate to prominent, dense peeling

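### The subject-level local skin reaction tables in SAP 7.9.8.4 ignore the Baseline score, so a reaction already present at entry can be counted as a post-baseline reaction

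*SAP*

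**What the plan says.** Protocol 9.4.5 defines five LSRs (burning/stinging, pruritus, erythema, dryness, peeling), each graded 0 to 3, and states: "All subjects will be assessed for LSRs, on the face, at each visit". Protocol 8.2 and Appendix 1 place one assessment at Baseline before the first dose; the others are at Weeks 1, 4, 8 and 12.

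SAP 7.9.8.4 plans four outputs:

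- A by-visit summary: "LSRs will be summarized by treatment group and visit using descriptive statistics".
- A worst-grade table: "Each subject's worst post-baseline grade for each LSR will also be summarized".
- An any-LSR table: "the number of subjects who experience mild, moderate or severe LSRs post-baseline will be presented".
- Listings of all LSRs and of subjects with severe LSRs.

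Neither the worst-grade table nor the any-LSR table is conditioned on the Baseline grade. There is no treatment-emergent definition, change from Baseline or shift table for LSRs. Protocol 11.12 adds none.

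Other safety sections of the SAP do use Baseline. Pre-existing adverse events (AEs) enter the summaries if they worsen (7.9.8.2). For laboratory tests, "shifts from Baseline to Week 12 in laboratory test results based on normal ranges will be summarized" (7.9.8.3). ECGs have shift tables and treatment-emergent categories (7.9.8.5.1), and vital signs have changes from Baseline (7.9.8.5.2).

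**The concern.** For a facial gel, the LSR tables are the main structured evidence on local tolerability against vehicle. As planned, a subject with grade 1 erythema before the first dose and grade 1 erythema at Week 1 is counted as having a mild post-baseline LSR. In the worst-grade table, a subject who goes from mild to moderate cannot be told apart from one who entered at moderate and stayed there.

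Some reactions at entry are plausible. Eligibility requires at least 20 inflammatory facial lesions (Protocol 5.3.1), grade 1 erythema is a very light pink (Protocol 9.4.5), and no criterion caps the LSR score at entry. At stake is how the tolerability comparison reads: signs present before dosing are mixed with reactions that arise on treatment.

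**Working it through.** The documents state no LSR rate, so there is no figure to reproduce. The textual check is the comparison above; the arithmetic below only illustrates the mechanism.

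**Inputs**

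- From the documents: 467 active and 233 vehicle subjects (SAP 4.1.2), all taken to be in the safety population.
- Assumed: Baseline prevalence b; probability q that a Baseline reaction is scored again after Baseline; new-onset rate i of 10% (active) and 5% (vehicle). Baseline-positive subjects are assumed not to worsen.

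**Formulas**

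- Planned any-LSR rate: b[q + (1−q)i] + (1−b)i, which simplifies to i + bq(1−i).
- New-or-worsened rate over all subjects: (1−b)i.

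For b = 20%:

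- q = 1: 0.10 + 0.20×0.90 = 28.0% active; 0.05 + 0.20×0.95 = 24.0% vehicle.
- q = 0.5: 0.10 + 0.10×0.90 = 19.0% active; 0.05 + 0.10×0.95 = 14.5% vehicle.
- New or worsened: 0.80×0.10 = 8.0% active; 0.80×0.05 = 4.0% vehicle.

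| b | Planned, q = 1 (ratio) | Planned, q = 0.5 (ratio) | New or worsened (ratio) |
|---|---|---|---|
| 0% | 10.0 vs 5.0 (2.00) | 10.0 vs 5.0 (2.00) | 10.0 vs 5.0 (2.00) |
| 20% | 28.0 vs 24.0 (1.17) | 19.0 vs 14.5 (1.31) | 8.0 vs 4.0 (2.00) |
| 40% | 46.0 vs 43.0 (1.07) | 28.0 vs 24.0 (1.17) | 6.0 vs 3.0 (2.00) |
| 60% | 64.0 vs 62.0 (1.03) | 37.0 vs 33.5 (1.10) | 4.0 vs 2.0 (2.00) |

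**Absolute difference.** The planned table shows (1−qb)(i_active − i_vehicle). At q = 1 this equals the new-or-worsened difference: 4.0, 3.0 and 2.0 points at b = 20%, 40% and 60%. At q = 0.5 and b = 20% the planned difference is 4.5 points, slightly larger, because it also counts reactions that clear and then recur.

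**Noise, b = 20%.** The standard error of the difference is:

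- Planned, q = 1: √(0.28×0.72/467 + 0.24×0.76/233) = 3.5 points.
- Planned, q = 0.5: √(0.19×0.81/467 + 0.145×0.855/233) = 2.9 points.
- New or worsened: √(0.08×0.92/467 + 0.04×0.96/233) = 1.8 points.

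**Chance Baseline imbalance.** The 95% range is 1.96×√[b(1−b)(1/467 + 1/233)]: ±6.3 points at b = 20% and ±7.7 at 40% or 60%. With no drug effect, an imbalance d moves the planned difference by dq(1−i). At b = 20% and i = 5% in both arms, that is 6.3×0.95 = ±6.0 points at q = 1, or ±3.0 at q = 0.5. The new-or-worsened count moves by only d×i = 6.3×0.05 = 0.3 points. This imbalance is a component of the noise above, not an addition to it.

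**Other onset rates.** With 30% vs 20% (ratio 1.50) and b = 20%, the planned table shows 44.0% vs 36.0% (1.22) at q = 1 and 37.0% vs 28.0% (1.32) at q = 0.5.

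**The case against.** The strongest reply is that this is a matter of presentation with limited consequence. Several parts of it stand.

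- **Size is not established.** The documents give neither b nor q. Protocol 1.2 reports erythema as the most common LSR in the dose-ranging study, but does not say that it was present at Baseline. Exclusion 4 (Protocol 5.3.2) and the washout periods limit signs at entry.
- **The absolute difference is not recovered.** A reader might infer that the planned tables hide part of the active-vehicle difference and that a new-or-worsened count would bring it back. The working does not support this: at q = 1 the two differences are identical. The gain is in the ratio, the precision and near-removal of Baseline imbalance.
- **The worst-grade table is less exposed.** Its moderate and severe rows are affected only by subjects who entered at those grades.
- **There are mitigations.** The by-visit summary should show Baseline distributions by arm, and every LSR is listed. LSRs experienced between visits, and severe visit-day LSRs, are recorded as AEs (Protocol 9.4.5).
- **Different formats are not a contradiction.** Shift tables for laboratory tests do not oblige the SAP to use them for LSRs.

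These points do not close the gap. The by-visit summary gives marginal distributions, which cannot show who worsened. The listing would require a reader to construct the count without a pre-specified rule. Visit-day grade 1 and 2 reactions never reach the AE tables. Randomization balances Baseline only on average and does not stop the ratio moving toward 1.

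**Conclusion.** The point holds as a modest gap in descriptive safety reporting. Both subject-level LSR tables count an unchanged Baseline reaction as post-baseline, although the score needed to separate the two is collected. The gap is mainly in visit-day grade 1 and 2 reactions.

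Its size cannot be fixed from the documents. Under the assumed 10% and 5% onset rates with b = 20%, the ratio of 2.0 appears as 1.17 (q = 1) or 1.31 (q = 0.5), and the standard error is 3.5 or 2.9 points rather than 1.8. If b = 0, nothing changes.

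A reader might go further and infer a biased safety conclusion or a threat to the efficacy result. The documents do not support either: Baseline imbalance under randomization has no expected direction, and SAP 7.9.8.4 plans no test of LSRs and no decision rule. No primary or secondary conclusion or error rate is involved.

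**What to change.** In SAP 7.9.8.4:

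1. Define a treatment-emergent LSR as a post-baseline grade higher than the subject's Baseline grade for that reaction.
2. Present the number and percent of subjects with a treatment-emergent LSR, by worst grade and arm.
3. Add, for each of the five LSRs and by arm, a shift table of Baseline grade by worst post-baseline grade.
4. Keep the planned tables. They still show the total burden, including reactions that clear and recur at the same grade, which the new definition would not count.

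The cost is a short change of SAP wording and one or two extra tables from data already collected. No new assessment is needed.
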